#### 6.1.17. Evaluation of Response

Evaluation of response will be conducted on Day 7 and every 7 days thereafter till Day 28.

## 6.1.17.1. Evaluation of Primary Endpoints

## 6.1.17.1.1. Safety and Tolerability Monitoring

For determination of the study's primary end point, evaluation of safety and tolerability will be conducted according to definitions and guidelines below.

Safety and tolerability will be assessed by the study medical staff (e.g., PI, site coordinator, and study nurse) and the study subjects on the basis of the following:

- 1. AEs and Serious Adverse Events (SAEs), including severity, relation to study treatment and classification by whether or not these events comprise intolerable side effects.
- 2. Physical exams, Draize score and vital signs measurements.

- 3. Urine testing.
- 4. Blood laboratory testing for changes in hematology and chemistry values.
- 5. ECG
- 6. Subjects questioning full medical history during screening, routine AE reporting and tolerability monitoring through review of subject's weight diary.

### 6.1.17.1.2. Efficacy Endpoint – Significant Thermogenesis

The study primary efficacy endpoint, a significant thermogenesis at the injected site will be evaluated by comparing with the contra-lateral, non-injected site. A significant thermogenic effect is defined as the increase of 1 °C from baseline in the difference in temperature (in °C) between the treated and not-treated sites (net delta). This thermogenesis should be apparent by 28 days after injection. The sites temperatures will be measured with a sensitive ( $\pm$  0.1 °C) Infra-Red thermal camera.

### 6.1.17.2. Evaluation of Secondary Endpoints

## 6.1.17.2.1. Sustained Thermogenic Effect

Sustained thermogenic effect will be evaluated by thermal imaging. A sustained thermogenic effect is defined as an evident thermogenic effect after 28 days. A significant thermogenic effect is defined as the increase of 1 °C from baseline in the difference in temperature (in °C) between the treated and not-treated sites (net delta). The duration of the thermogenic effect will be evaluated in the lower dose groups till Day 56 and in the higher dose groups by thermal imaging every 28 days in those subjects demonstrating clear thermogenesis by 28 days after injection for a maximum period of an additional 5 months.

#### 6.1.17.2.2. Local Fat Mass Reduction

Local reduction in fat mass will be evaluated by MRI. A local fat reduction is defined as a significant reduction (compared to baseline) in the average width of abdominal subcutaneous fat in the injected area compared to the contra-lateral area, SFM ratio, as evaluated by MRI. Local fat reduction in cohort 4 will be defined as a significant reduction (compared to baseline) in the average width of abdominal subcutaneous fat in the injected area compared to the surroundings area, SFM ratio, as evaluated by MRI. MRI will be evaluated in all groups at baseline and at Day 28. MRI will be evaluated in the cohort 3 (or in cohort 2 if 2 subjects will experience intolerable side effects within the 3rd cohort) and cohort 4 every 28 days for up to 6 months from the beginning of treatment.

### 6.1.17.2.3. Clinical Laboratory Changes

Clinical Laboratory Changes will be evaluated comparing to baseline. Clinical laboratory changes definition is a significant change from baseline according to the laboratory normal

ranges that affect the subject's medical status as assessed by the investigating physician, including improvement in fasting glucose and lipid profile.

### 6.1.17.2.4. Anthropometric Measurements Change

Anthropometric measurements will be evaluated comparing to baseline. Anthropometric measurements changes are defined as significant reduction in body weight, BMI and WHR at the end of the study compared to baseline.

## 6.1.17.2.5. Histological Changes

Histological changes will be evaluated comparing to known historical data. Histological changes definition is an evident change from known historical data of normal subcutaneous adipose tissue as assessed by an expert pathologist.

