#### Follow-up visits (Day 29-168):

Subjects of the 1st and 2nd cohorts:

- On visit Day 56 will come after overnight fast (10-12hr fast) for the glucose, insulin, lipid profile tests and FFA levels. Subjects will be followed up for anthropometric measurements, thermal imaging and adverse events. An MRI scan will be conducted on Day 56 in subjects of the 2nd cohort.
- Will continue to be followed for safety every 28 days till Day 112. If Draize-score is 0 for edema and erythema by visit Day 56 then subjects will be followed by phone call for AE.

Subjects of the 3rd and 4th cohorts (or treated with the highest dose achieved):

- Will be followed up for anthropometric measurements (e.g., BMI, WHR) every 28 days as long as the thermogenic effect is apparent and for a period that will not exceed 6 months from the beginning of treatment.
- Subjects will record their weight following 10-12hr fast (overnight) fast and at bedtime once a week when not visiting the site, in a diary. Diaries will be checked and data will be captured in the CRFs.
- In addition, evaluation of the injected area and the contra-lateral side will be performed by Draize score, photographs and thermal imaging
- Subjects will come fasting (10-12hr fast) for the glucose, insulin, lipid profile tests and FFA levels.
- MRI of 16 slices that includes the injected site (SAT evaluation). MRI will be conducted on Day 28 days and every 28 days for a period that will not exceed 6 months from the beginning of treatment in the 3rd and 4th cohorts.
- On Day 56 (following MRI), in 3 randomly selected subjects treated with the 3rd cohort (2 RZL-012 treated that show a sustained thermogenic effect by thermal camera imaging and one subject treated with vehicle with no thermogenic effect), an abdominal subcutaneous (SC) adipose tissue biopsy will be taken from the injected side. The biopsy site will be anesthetized with 1% lidocaine and will be performed by a trained medical professional. The sample (an elliptical excision of 15-20mm deep and 4.5-6cm long) will be placed in a vial filled with a fixation solution (formaldehyde). After 24h ± 2h, the fixation solution should be exchanged to ethanol 80% and further processed for histological analysis. Biopsies will be stained for hematoxylin and eosin (H&E) and further evaluated for BAT

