#### **6.1.14. Biopsy**

On Day 56 (following MRI), in 3 randomly selected subjects of the 3rd cohort (or the 2nd if 2 subjects experience intolerable side effects in the 3rd cohort) an abdominal SC adipose tissue biopsy will be taken from the injected side. The Sponsor or designee will select 3 subjects to go under a biopsy: two subjects who will be demonstrating clear thermogenesis (assuming an active) and one subject who will not demonstrate thermogenesis (assuming a control). Before biopsy the Sponsor representative who is un-blinded to the study will confirm that the selected subjects are indeed 2 RZL-012 treated and 1 vehicle treated. Subjects will be followed 7 days post biopsy and will terminate their study participation.

After local anesthesia, an elliptical excision biopsy will be conducted by a trained medical professional 10 cm lateral to the umbilicus lateral wall (Figure 2). A sample of fat tissue (a biopsy of an ellipse of 15-20 mm deep and 4.5-6 cm long, Figure 2) will be taken from the incision. For optimal cosmetic results the incision will be made on a slant following Langer's lines. The incision will be stitched appropriately and the wound will be covered with a bandage or sterile dressing. The sample will be divided in two. One half will be placed in a vial filled with a fixation solution (formaldehyde). After 24h ± 2h, the fixation solution should be exchanged to ethanol 80% and further processed for histological analysis. Each vial and lid will be labeled with: subject's name, subject's identification number and biopsy site. The other half of the biopsy will be embedded in a labeled cryomold with Optimum Cutting Temperature (OCT) compound and flesh frozen using a cryostat or liquid nitrogen. Each sample will be labeled with: subject's name, subject's identification number and biopsy site. Biopsies will be sent to the sponsor in an adequate manner and evaluated by a certified pathologist. Biopsies will be stained for hematoxylin and eosin stain (H&E) and further evaluated for BAT and other markers and morphometry.

Figure 2: Biopsy Site and Dimensions

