- 5.8.3 Kruskal-Wallis will be used to compare the net-delta between the study arms for the relevant cohorts and visits.
- 5.8.4 The number and percent of subjects with a thermogenic effect, defined as a net-delta ≥ 1, will be presented by cohort and visit for the subjects in the active arm. The duration of the thermogenic effect after the Day 28 visit, for subjects in the active arm with thermogenic effect at the Day 28 visit will be presented.
- 5.8.5 Subcutaneous Fat Mass (SFM) ratio (treated sites / control sites) averaged over the MRI slices will be presented in tabular form by visit, treatment and cohort. The change from baseline in this ratio (in % from the ratio at baseline) will be presented in the same manner, and compared between the treatment arms with Kruskal-Wallis test.
- 5.8.6 Changes from baseline in fasting blood glucose, lipid profile, anthropometric changes, inflammatory markers and cytokines will be presented by visit, treatment, and cohort.
- 5.8.7 Histology results will be presented in tabular form by treatment for relevant subjects.
- 5.8.8 Safety analysis
- 5.8.9 Safety data will be summarized for the Safety population.
- 5.8.10 Adverse events will be coded according to coding dictionaries (the most updated version of MedDRA) and presented in tables by System Organ Class (SOC) and Preferred Term (PT) and by treatment group.

- 5.8.11 The incidence of AEs, as well as the intensity and relationship to study drug will be summarized by treatment group.
- 5.8.12 The incidence of all adverse events will be presented by treatment overall and by cohort along with two sided 95% exact binomial Confidence Interval (CI).
- 5.8.13 The incidence of intolerable side effects will be presented by treatment overall and by cohort along with two sided 95% exact binomial Confidence Interval (CI).
- 5.8.14 Concomitant medication verbatim terms (as recorded on the CRFs) will be coded to Anatomical Therapeutic Chemical (ATC) Level 2 and 4 using the World Health Organization (WHO) dictionary.
- 5.8.15 Interim Analysis
- 5.8.16 An interim analysis is planned at the end of each cohort for evaluation of efficacy. For this purpose, a data lock (except for externally collected data such as PK) will be implemented after each cohort is completed. Upon lack of trends in efficacy due to effect size, the Sponsor will consider study termination

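### The histology endpoint is defined against historical, uninjected fat and leaves out the concurrent vehicle biopsy, whose donor is also chosen for showing no heat

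*Protocol*

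**What the plan says.** Protocol section 4.2 lists, sixth of seven secondary endpoints, the tissue changes that explain the thermogenic effect. Section 4.1 names biopsy among the results supporting the primary efficacy evaluation. Section 6.1.17.2.5 sets the comparator, "Histological changes will be evaluated comparing to known historical data", and gives the only definition: "Histological changes definition is an evident change from known historical data of normal subcutaneous adipose tissue as assessed by an expert pathologist". It does not mention the vehicle biopsy.

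Section 6.1.14 takes three biopsies at Day 56 in cohort 3 (cohort 2 as fallback), from the injected side only. The sponsor or its designee chooses "two subjects who will be demonstrating clear thermogenesis (assuming an active) and one subject who will not demonstrate thermogenesis (assuming a control"), and an unblinded sponsor representative "will confirm that the selected subjects are indeed 2 RZL-012 treated and 1 vehicle treated". The Synopsis, under follow-up visits, likewise asks for "one subject treated with vehicle with no thermogenic effect". Both places nevertheless call the selection random; section 6.1.14 has the biopsies taken "in 3 randomly selected subjects of the 3"rd cohort. Footnote k of Appendix I, repeated in SAP section 5.4.4, makes the biopsies depend on thermogenesis being visible.

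Under section 6.2.3.2 each cohort has two vehicle subjects, injected in the same way as the active subjects. Specimens are labelled with name, identification number and site, and are read for BAT markers and morphometry as well as by H&E (section 6.1.14). Protocol section 10.5.5 plans a table by treatment, and SAP section 5.8.7 says: "Histology results will be presented in tabular form by treatment for relevant subjects". No section says that the pathologist is masked.

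**The concern.** The endpoint is meant to identify the tissue change that goes with RZL-012. Fat that has never been injected cannot separate the drug from its vehicle or from the needles. The vehicle biopsy can, but it has no role in the definition.

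The definition also names no feature, so inflammation, fibrosis or fat necrosis would satisfy it. Section 4.1, by contrast, requires the thermogenic effect to be unrelated to inflammation.

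The choice of vehicle subject adds a second, conditional problem. A vehicle subject who warms cannot serve as the control. If warmth follows local injury, the control is then steered towards normal tissue.

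These three specimens matter more than their number suggests. Section 1.2.4 reports that the phase 0 biopsies yielded too little tissue to show remodelling.

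**Working it through.** The documents give no sample size, error rate or effect size for histology, so there is no planned figure to reproduce. The only count is 2 RZL-012 + 1 vehicle = 3 biopsies, which is consistent.

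**Step 1: exposure.** In cohort 3, active and vehicle subjects alike receive 24 × 0.1 mL = 2.4 mL; in the cohort 2 fallback, 16 × 0.1 mL = 1.6 mL (section 6.2.3.1). The ellipse is 4.5–6 cm long (6.1.14) and the cohort 3 field is 12 × 8 cm (3.3.2), so a specimen covers only part of the field. Section 7.2 lists, from animal studies, inflammation in adjacent fat still present at 56 days, but does not isolate the vehicle.

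**Step 2: what the definition counts.**

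| Active changed | Vehicle changed | Active biopsies meeting 6.1.17.2.5 | Reading against vehicle |
|---|---|---|---|
| 2/2 | 1/1 | 2/2 | Same finding in both arms; only type and grade can differ |
| 2/2 | 0/1 | 2/2 | Finding in active only |

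The definition returns the same answer in both rows.

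**Step 3: how often this could happen.** Assume no drug effect on tissue, and let q be the chance of an injection- or vehicle-related change at Day 56. Before any selection on heat, P(at least one of two active biopsies changed) = 1 − (1 − q)²:

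- q = 0.1: 1 − 0.81 = 0.19
- q = 0.25: 1 − 0.5625 = 0.44
- q = 0.5: 1 − 0.25 = 0.75
- q = 0.75: 1 − 0.0625 = 0.94

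**Step 4: selection on heat.** Let h1 = P(hot | injury) and h0 = P(hot | no injury), both assumed. By Bayes' rule, P(injury | hot) = q·h1 / [q·h1 + (1 − q)·h0], and similarly for cold subjects. Take q = 0.5, h1 = 0.6, h0 = 0.1:

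- P(hot) = 0.30 + 0.05 = 0.35
- P(injury | hot) = 0.30 / 0.35 = 0.857
- P(injury | cold) = 0.20 / 0.65 = 0.308
- P(2/2 active changed, vehicle unchanged), all three selected on heat = 0.857² × 0.692 = 0.51
- The same with no selection = 0.5² × 0.5 = 0.125
- The same with active subjects chosen hot but the vehicle subject drawn at random = 0.857² × 0.5 = 0.37

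Over q = 0.25 to 0.75 and h1 = 0.3 to 0.6, with h0 = 0.1, full selection gives 0.20 to 0.51, against 0.05 to 0.14 with none. In the worked case, choosing a cold control accounts for the step from 0.37 to 0.51; the rest comes from choosing hot active subjects. With h1 = h0 the effect is nil.

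**Step 5: what two against one can show.** The most extreme split, 2/2 against 0/1, has Fisher p = 1/3 = 0.33. The exact 95% interval for 0/1 runs from 0 to 0.975. No choice of comparator makes this inferential.

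**The case against.** The strongest reply is that the analysis plan already handles this. Histology is tabulated by treatment, and SAP section 5.8.4 puts the SAP above the protocol on how data are analysed. The SAP has no historical-comparator rule. This stands in part: the vehicle result will be shown. But the SAP supplies no definition of its own, so the protocol's remains, and the Appendix I list of table shells has no histology entry.

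Three stronger readings are tempting, and the documents do not support them.

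- *Change in all three biopsies would be reported as a drug effect.* The planned table would show 2/2 active beside 1/1 vehicle, which openly indicates non-specific change. The fault is in the definition; the vehicle result is not hidden.
- *Choosing a cold control makes the drug–heat link circular.* That link comes from comparing net-delta between arms (protocol 10.5.5, SAP 5.8.3). The biopsies ask what tissue accompanies the heat, and sampling warm treated tissue for that is defensible. The control is negative on thermography only; its histology can still show injury.
- *Half the possible controls are discarded.* That holds only if exactly one of the two vehicle subjects is warm. If both are cold, none is excluded; if both are warm, no eligible control remains. Section 1.2.4 reports warming in treated subjects only in phase 0, at lower doses, so two cold controls are plausible.

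Two further points stand. BAT markers and morphometry are harder to attribute to needle damage, although the definition does not require them. And a strict rule of present in active, absent from vehicle would let one specimen decide. With no drug effect and q = 0.5 it would still be met with probability 0.75 × 0.5 = 0.375, and it would score a real but graded effect as none.

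**Conclusion.** The point holds in a limited form. Section 6.1.17.2.5 lets a needle or vehicle change in an RZL-012 biopsy meet the endpoint definition, and the by-treatment table does not alter that. This part follows from the text alone. How often it would occur depends on q, which the documents do not give: 0.19 to 0.94 for q from 0.1 to 0.75.

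Selecting the vehicle subject for absence of heat contradicts the stated random selection and does not fit footnote k. It could bias the control towards normal tissue, but the size is unknown. It is nil if heat is unrelated to injury, or if both vehicle subjects are cold.

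The matter concerns a descriptive secondary endpoint with three specimens. It is worth correcting because section 4.1 relies on biopsy as support for the primary efficacy evaluation and the correction is cheap.

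**What to change.** - In section 6.1.17.2.5, make the concurrent vehicle biopsy the primary comparator. Report the type and grade of each finding, BAT markers and morphometry included, for active against vehicle, with historical data as background. Do not require that a finding be absent from the vehicle specimen.
- Have the same pathologist read slides coded without subject name, arm or thermal result.
- Have the unblinded representative draw the vehicle subject at random from the cohort's two, whatever the thermal image shows. Reconcile the Synopsis, section 6.1.14 and footnote k (also in the SAP) accordingly, and say plainly that the two active subjects are chosen on heat if that is kept.
- In SAP section 5.8.7, state that two against one is descriptive and supports no inference, and add a histology shell to Appendix I.

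The cost is wording and slide labels, with no extra biopsy or reader. The downside is that the statement rests on one vehicle specimen. A random draw of the control also leaves in place whatever bias comes from choosing warm active subjects.

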## 6.1.17.2.6. Inflammatory Markers and Cytokines Changes

To determine drug mechanism of action, inflammatory markers and cytokines level in cohorts 2 through 4 will be evaluated by comparing to baseline. Inflammatory markers and cytokines changes definition is an apparent change from baseline.

### 6.1.17.3. Compliance Monitoring

Compliance monitoring will include the following procedures:

- Compliance assessment by site coordinator at the study visit, including but not limited to subject questioning and review of the weight diary completed by the subject.
- Completion of weight diary by the subject.

### 6.1.17.4. Dispensing of RZL-012 Investigational Product

The RZL-012 investigational product will be dispensed to the study site under monitored conditions by Nextar Ltd. All procedures connected to investigational product's allocation (kits received at site, returned kits) will be properly documented, dated and signed in a designated site folder to allow full product tracking. Source documents will be kept for the duration required by local regulations and ICH-GCP (whichever is longer).

### 6.1.17.5. Questioning of Study Subjects

Questioning of study subjects during site visits and any unscheduled conversations (e.g., by phone) with site staff will be fully documented in subject file. Whenever possible, subject questioning should include, but not be limited to, inquiring information regarding occurrence and severity of AEs, treatment tolerability and compliance to future scheduled procedures and visits.

#### 6.2. STUDY VISITS

Study visits will be fully documented in the CRF as described in Section 11. Documentation will be completed in a timely manner and within 5 working days to ensure protocol adherence and compliance with ICH-GCP.

### **6.2.1.** Screening Procedures

All information collected and documented during screening procedures will be reviewed to ensure eligibility in reference to study inclusion and exclusion criteria, and fully documented in subject file.

Screening visit Day 1 should be performed no later than 7 days prior to baseline visit for all cohorts.

Subjects should be notified to come fasting (10-12 hours of fast) for the fasting glucose test and weight measurement. Subjects screening visit Day 2 should be performed no later than 2 days prior to baseline visit. Subjects who are alternates, and not dosed, the screening visit Day 2 should be performed no later than 12-14 days prior to baseline.

Study screening Day 1 procedures will include the following:

- Informed Consent Section 6.1.1
- Medical History Section 6.1.2
- Concomitant Medication Section 6.1.3
- Physical Examination Section 6.1.4
- Vital Signs and Measurements Section 6.1.5
- Anthropometric Measurements Section 6.1.6
- Serology Assays Section 6.1.7
- Clinical Laboratory Tests Section 6.1.8
- ECG Section 6.1.9
- Draize Score Section 6.1.10
- Photography of Injected Site Section 6.1.11
- Thermal Imaging- Section 6.1.12
- Fasting glucose

Subjects may be rescreened if they were screened and not dosed within 14 days. The following procedures will be performed: Clinical Laboratory Tests (hematology, serum chemistry, and

urinalysis), vital signs, weight, BMI, waist and hip circumference WHR, Draize score, photography and thermal imaging.

Study screening day 2 procedure will include the following:

- Anthropometric Measurements Section 6.1.6
- Fat Tissue Imaging: Magnetic Resonance Imaging (MRI) Section 6.1.13

### 6.2.2. Study Randomization

Subjects will be randomized to each study group, i.e., investigational therapy or control, left side injection or right side injection according to a predefined randomization scheme. The investigational therapy group will be treated with RZL-012 and the control group will be treated with the same formulation (vehicle) as with RZL-012, absent active medication.

Masking will be used to blind the Investigator regarding randomization, i.e., assignment to study group will be disclosed only after subject eligibility is confirmed and immediately before treatment initiation. The pharmacist will be unmasked and will be responsible to fill the syringes for injection.

